Study Significance: The large bony and soft tissue tumor resections performed in musculoskeletal oncologic patients presents the potential for significant blood loss. With basic arthroplasty being associated with significant intraoperative and postoperative blood loss often necessitating blood transfusion¹, larger bony resections with the use of endoprostheses presents an even higher risk². Transfusions themselves are not without known complications. Examples include infection, hemolytic transfusion reaction, and increased short-term mortality^{1,3}. Tranexamic acid (TXA), a synthetic analog of lysine, is an antifibrinolytic that is used to reduce blood loss. TXA works by blocking the lysine binding sites on plasminogen⁴. Perioperative use of TXA has been shown to decrease intraoperative and postoperative blood loss and decrease transfusion rates in both total knee arthroplasty and total hip arthroplasty⁵⁻¹⁵. It has also been shown to result in higher postoperative hemoglobin¹³. TXA also has been shown to decrease postoperative pain, swelling, length of hospital stay, and result in higher patient satisfaction¹⁶. The proposed research is intended to show if any correlation exists between administration of TXA or not to musculoskeletal oncology patients undergoing endoprosthetic reconstruction and perioperative blood loss and blood transfusion rates. The results of this study are

important because it will serve to fill the void in the current literature as there is no current literature available that has studied TXA administration in this specific patient population.

There have been several papers written with regards to the safety of TXA in high risk patients (i.e. previous PE/VTE event).^{21,22} Whiting et al showed that in high risk patients (defined as American Society of Anesthesiologists score of III or IV) , TXA was not associated with an increase in symptomatic thromboembolic events and was associated with a decrease in transfusion rates.²² Sabbag et al showed that patients with a history of VTE had a low risk of recurrent VTE (2%) after contemporary total hip arthroplasty and total hip arthroplasty, and that rate was not increased with the use of IV TXA.²¹

Literature Review

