
utilized. We also plan to record patient specific factors including age, sex, smoking status, BMI, pre-op diagnosis, operative time, comorbidities, and length of stay. These variables will be analyzed independently to detect any correlation with perioperative blood loss and erythrocyte transfusion rate.

C. Sample size, statistical methods, and power calculation

Method of Randomization: Patient randomization will be done via a randomization program through REDCap. The randomization process will be performed centrally at Kansas University Medical Center and the treating surgeon will not have access to the randomization list. Randomization will occur prior to definitive surgical procedure, and the treating surgeon and pharmacy will be notified to ensure adequate vials of tranexamic acid are available in the operating room (investigators/surgeons are not blinded). Patients will be blinded to treatment allocation. Treatment assignments will be stratified by type of resection. A power of 0.9 would require a total of 40 patients (20 per treatment group) be enrolled in the bony tumor group and 100 patients (50 per treatment group) in the soft tissue tumor group.

Since we are gathering entirely objective data the treating surgeon does not need to be blinded. Group differences in preoperative hemoglobin and hematocrit, transfusion requirements, drain output at 24 hours, and changes in hemoglobin and hematocrit will be compared using pairwise Student T-test analysis. Pairwise T-tests between each of the groups (for continuous variables) and Chi squared analysis (for categorical variables) will be used to determine if a statistically significant difference exists between the groups in terms of the patient specific factors that are also collected and analyzed (age, sex, smoking status, BMI, operative time, length of stay).

D. Subject Criteria (See Vulnerable Populations appendix, if applicable):

Inclusion criteria: Patients (male or female) between the ages of 18-90 undergoing wide resection of a malignant bony tumor of the lower extremity with endoprosthetic reconstruction or resection of soft tissue sarcoma measuring >5cm.

Exclusion criteria:

- Patients undergoing revision endoprosthetic reconstruction
- Patients with known coagulopathy
- Known history of DVT or embolic disease
- Benign tumors
- Patients with allergy to TXA
- Those refusing blood products
- Those concurrently on anti-coagulant therapy
- Pregnant and nursing women

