1. Describe steps to be taken to assure that the data collected are accurate, consistent, complete and reliable. (source data verification, audits or self – assessment) Source data verification and self-audits will be performed. The protocol for the clinical trial will be spelled out for the participants. A discussion will be had between the PI at KUMC and the PI at the participating institution to ensure the protocol is understood.

V. Data Analysis and Reporting

A. Statistical and Data Analysis: Group differences in preoperative hemoglobin and hematocrit, transfusion requirements, drain output at 24 hours, difference in hemoglobin balance method, and changes in hemoglobin and hematocrit will be compared using pairwise Student T-test analysis. Pairwise T-tests between each of the groups (for continuous

variables) and Chi squared analysis (for categorical variables) will be used to determine if a statistically significant difference exists between the groups in terms of the patient specific factors that are also collected and analyzed (age, sex, smoking status, BMI, operative time, length of stay, presence of coagulopathy, specific anticoagulation regimen should it differ from study protocol, size of resection, depth of resection, location of tumor, pathologic diagnosis, stage of disease).

B. Outcome: We expect the results to be similar to the TXA arthroplasty studies/literature with regards to decreased perioperative blood loss and decreased transfusion rates. There are not necessarily any criteria for success or failure. The results of this study will help provide a definitive answer regarding the safety and efficacy of TXA in oncologic patients. This will help unify the musculoskeletal oncology field in their use or abandonment of TXA.

C. Study results to participants: The study results/conclusions will not be given to subjects unless they are specifically asked for at future scheduled outpatient clinic visits. Once the proposed study is completed a conversation with subjects can occur on an outpatient basis at their routine scheduled clinic visits regarding our results and conclusions if desired. The subjects reserve the right to know what conclusions were drawn from the study they directly participated in. In addition, we plan to publish a manuscript with our results/conclusions after completion of the study which can be sought after if desired.

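### Patient factors are to be correlated with blood loss one at a time, with no allowance for resection type; if bone and soft-tissue patients are pooled, the operation can pass for a patient factor

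*Combined protocol and SAP*

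**What the plan says.** Section II.B states: "We also plan to record patient specific factors including age, sex, smoking status, BMI, pre-op diagnosis, operative time, comorbidities, and length of stay". It continues: "These variables will be analyzed independently to detect any correlation with perioperative blood loss and erythrocyte transfusion rate". That is the whole specification of the factor analysis. No model, covariate, stratum or pooling rule is given.

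The methods in II.C and V.A are t-tests and chi-squared tests: "changes in hemoglobin and hematocrit will be compared using pairwise Student T-test analysis". Where those sections mention patient factors, the tests compare the factor between study groups. They do not estimate how a factor relates to blood loss or transfusion.

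Resection type does enter the design. Under II.C, "Treatment assignments will be stratified by type of resection", with separate sample sizes for the bone stratum ("A power of 0.9 would require a total of 40 patients (20 per treatment group) be enrolled in the bony tumor group") and the soft-tissue stratum ("100 patients (50 per treatment group) in the soft tissue tumor group"). No planned analysis uses it as a covariate.

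**The concern.** The trial enrols patients having two unlike operations: bone resection with an endoprosthesis, and resection of a soft tissue sarcoma. If the operations differ in blood loss and also in a listed factor, correlating the two across all patients picks up the operation. The factor may have no relation to bleeding among patients having the same operation and still be reported as associated with it.

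Three of the eight factors need particular care.

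- **Pre-op diagnosis.** Patients qualify with either a malignant bony tumor or a soft tissue sarcoma, so diagnosis largely encodes resection type.
- **Operative time.** II.C says "Randomization will occur prior to definitive surgical procedure", so this is measured after allocation and is not a baseline characteristic.
- **Length of stay.** This too is measured after allocation. Section I.B says of TXA in arthroplasty that "TXA also has been shown to decrease postoperative pain, swelling, length of hospital stay". Heavy bleeding may itself prolong the stay. Under II.B and II.E, a patient discharged before day 3 has no further blood draws, so length of stay also determines which hemoglobin values exist.

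At stake is the secondary message of the paper: which patients bleed more or need transfusion.

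**Working it through.** **Plan's own figure.** There is none for this analysis. The power statement gives only 2 × 20 = 40 and 2 × 50 = 100 patients, 140 in all, at power 0.9. It cannot be recomputed, because no alpha, effect size or SD is stated. Back-solving at two-sided 0.05 gives (1.96 + 1.28) × √(2/50) = 0.65 SD for 50 per arm. I use that only as an assumed TXA effect on blood loss below.

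**Inputs.** From II.C: 40 bone and 100 soft-tissue patients, so p = 40/140 = 0.286 and q = p(1 − p) = 0.204. Assumed: two-sided alpha 0.05, zero correlation within each resection type, and bone minus soft-tissue differences of dY in blood loss and dX in the factor, in within-type SD units.

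**Step 1: correlation created by pooling.**

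r = q·dY·dX / √[(1 + q·dY²)(1 + q·dX²)]

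For dY = dX = 1: r = 0.204/1.204 = 0.169. For dY = dX = 0.5: r = 0.051/1.051 = 0.049.

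**Step 2: how often it is significant.** By the Fisher transformation, z = atanh(r) × √(140 − 3), and the rate is P(Z > 1.96 − z) + P(Z < −1.96 − z). For dY = dX = 1, z = 0.171 × 11.70 = 2.00, which gives 52%. Simulation (20,000 runs) with and without the assumed TXA effect agrees:

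| dY, dX (SD) | r | Formula | Simulated, no TXA effect | Simulated, TXA effect −0.65 SD | Simulated, adjusted for type and arm |
|---|---|---|---|---|---|
| 0, 1 | 0 | 5% | 5% | 5% | 5% |
| 0.5, 0.5 | 0.049 | 9% | 9% | 8–9% | 5% |
| 1, 1 | 0.169 | 52% | 53% | 50% | 5% |
| 1.5, 1.5 | 0.315 | 97% | 98% | 97% | 5% |

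A TXA effect adds variance to blood loss and slightly dilutes the pooled correlation, hence 50% rather than 53%.

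**Step 3: pre-op diagnosis.** Take the limiting case in which diagnosis is identical to resection type. The test is then a bone v soft-tissue comparison with noncentrality d × √(40 × 100/140) = 5.35d. It is significant 36%, 76% and over 99% of the time for assumed blood-loss differences of 0.3, 0.5 and 1.0 SD. Such a difference is real, but it would be labelled an effect of diagnosis.

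**Step 4: TXA arm.** Arm is allocated within resection type, so it is independent of baseline factors by design. With no difference between resection types and a factor that TXA does not affect, ignoring arm leaves the rate at 5%. If TXA lowers the factor by an assumed 0.3 or 0.5 SD, which is possible only for operative time or length of stay, ignoring arm gives 8% or 14%. Adjusting for arm returns it to 5%. Adjusting for arm alone does not cure the problem in Step 2: the rate at (1, 1) is still 53%.

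These runs concern blood loss. The transfusion outcome was not simulated; the same mechanism applies, but no rate is claimed for it.

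**The case against.** The plan is organised around four groups, with separate sample sizes for bone and soft tissue. An analyst could reasonably run the correlations within resection type, and then the pooled rates do not apply. The word used for the approach is also ambiguous. This stands: the documents do not establish pooling, so the point is conditional.

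The stated aim is only to find correlations. If bone resections take longer and bleed more, operative time and blood loss are truly correlated in the pooled sample. The rates above are false positives only against a null of no association within each resection type. That is fair. However, an association that merely restates which operation was done says nothing about the patient, and the plan calls these patient-specific factors.

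The SD differences are assumed, and no basis exists for expecting 1 SD in, say, sex or BMI. This stands, which is why the 9% and 5% cases are shown beside the larger ones. The support in I.B for an effect of TXA on length of stay comes from knee arthroplasty, not this population.

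Comparisons of operative time and length of stay between groups are already planned in II.C and V.A. This stands; no new comparison is needed for them.

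A reader might go further and infer that spurious predictors are bound to appear, that leaving out TXA arm confounds all eight factors, or that the main trial result is compromised. The documents support none of these. Pooling is not stated and no differences are quantified. Arm is randomised within resection type. The factor correlations are neither a primary nor a secondary outcome.

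**Conclusion.** The point holds as a conditional one. The plan specifies one-at-a-time correlations and nowhere adjusts for or stratifies by resection type. If the 140 patients are pooled, the false-positive rate for a factor with no within-type association runs from 5% (no difference between types in either variable) through about 9% (0.5 SD in both) to about 53% (1 SD in both). It returns to about 5% once resection type is in the model. These figures rest on assumed SD differences and an assumed two-sided alpha of 0.05; the documents give neither.

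Omitting TXA arm leaves the six baseline factors unbiased and matters only for operative time and length of stay. The randomised TXA comparison is untouched. This is a low-cost improvement to a subsidiary analysis, not a flaw in the trial's main inference.

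**What to change.** In II.B, replace the sentence on analysing the factors independently with text such as:

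> Each baseline factor's association with blood loss (linear model) and with transfusion (logistic model) will be estimated with resection type and TXA arm in the model, reported with a 95% CI and labelled exploratory. Pre-op diagnosis will be examined only within resection type. Operative time and length of stay will be treated as post-randomisation outcomes, using the between-group comparisons already planned, within resection type, and not as patient predictors.

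The cost is a few lines of text. Resection type and arm are already recorded, so no new data are needed. The downside is that fewer factors will look significant.

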NCT04347122

Tranexamic Acid in Radical Resection and Endoprosthetic Reconstruction Protocol

Dec 17, 2019

University of Kansas Medical Center
RESEARCH PROTOCOL INVOLVING HUMAN SUBJECTS TEMPLATE
WITH GUIDANCE

Version date: 12/17/2019

Principal Investigator: [name] MD, Assistant Professor of Orthopaedic Surgery

Study Title: Tranexamic Acid in Radical Resection and Endoprosthetic Reconstruction: A Randomized Controlled Trial

Co- Investigator(s): [name] MD, [name] MD, [name] MD

I. Purpose, Background and Rationale A. Aim and Hypotheses

Resection of bony and soft tissue tumors with endoprosthetic reconstruction presents a significant risk of perioperative blood loss requiring transfusion. As transfusions are known to have inherent risks, a goal of therapy is to minimize perioperative blood loss. Tranexamic acid (TXA) is an antifibrinolytic that is commonly used to reduce blood loss in orthopaedic procedures, most often arthroplasty. The safety (even in patients with significant comorbidities) and efficacy of TXA in joint arthroplasty is well documented in the literature. There is, however, a dearth of literature exploring the safety and efficacy of TXA in musculoskeletal oncologic patients.

The aim of this study is to determine in a randomized controlled fashion if there is any difference in perioperative blood loss and blood transfusion rates when tranexamic acid is used compared to when it is not used in patients undergoing radical resection of bone and soft tissue sarcomas with endoprosthetic reconstruction. Hypotheses: (1) TXA will decrease perioperative blood loss. (2) TXA will decrease blood transfusion rates. (3) TXA will decrease post-operative surgical drain output.

B. Background and Significance

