is not used in patients undergoing radical resection of bone and soft tissue sarcomas with endoprosthetic reconstruction. Statement of Purpose: to determine in a randomized controlled fashion if there is any difference in perioperative blood loss and blood transfusion rates following radial resection of malignant bony tumors with endoprosthetic reconstruction when TXA is used compared to when it is not. Primary outcome measure: determination of perioperative blood loss. To do this, values will be recorded preoperatively and compared to post-operative values. Perioperative blood loss will be calculated using the Hemoglobin balance method.²³⁻²⁶ Secondary outcome measures: (1) Blood transfusion rates. (2) Surgical drain output.

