B. Study Type and Design: Type of Study: multi-center prospective randomized controlled trial. Study Design: We will initially monitor 4 groups of patients. The first group (20 patients) will undergo bony tumor resection of the femur or proximal tibia and endoprosthetic reconstruction with TXA. The second group (20 patients) will undergo bony tumor resection of the femur or proximal tibia and endoprosthetic reconstruction without TXA. The third group (50 patients) will undergo soft tissue sarcoma resection of the lower extremity with TXA. The fourth group (50 patients) will undergo soft tissue sarcoma resection of the lower extremity without TXA. The use of TXA is well established for arthroplasty at this institution given the body of evidence supporting both efficacy and safety. Treatment assignments will be stratified by type of resection location. Patient randomization will be done via randomization program through REDCap. The randomization process will be performed centrally at Kansas University Medical Center and the treating surgeon will not have access to the randomization list. Randomization will occur prior to definitive surgical procedure, and the treating surgeon and pharmacy will be notified to ensure adequate vials of tranexamic acid are available in the operating room (investigators/surgeons are not blinded). Patients will be blinded to treatment allocation. Those in groups using TXA will receive 1g TXA IVPB 10 minutes prior to incision and a second dose of 1g IVPB at the time of closure which is the standard protocol used for total joint arthroplasty. The TXA will be administered by the anesthesia team. If the surgeon determines intraoperatively that TXA is required for patient safety, the drug should be used. Patients receiving a non-standard dosing of TXA will then be excluded from the study. Routine hemoglobin and hematocrit measurements will be observed preoperatively as well as postoperatively at 6 hours and in the mornings of postoperative days 1-3. This laboratory regimen is currently the standard of care and utilized routinely. Patients may be discharged prior to obtaining all 4 blood draws. If a patient is discharged prior to postoperative day 3, no additional blood draw will be performed. Additionally, both intraoperative and postoperative incidents of blood transfusion will be monitored to calculate transfusion rates. Postoperative erythrocyte transfusions will be given for hemoglobin below 7.0 as is the current practice guidelines used by the attending surgeons at this institution. Other facilities are encouraged to follow this protocol, however, the ultimate decision for blood transfusion will be at the discretion of the treating physician. Surgical drains are also used routinely and their daily output will be recorded until they are deemed appropriate to pull by the attending surgeon. Patients will be clinically monitored daily while in the hospital and in subsequent follow up visits for symptoms of DVT or embolism and appropriate diagnostic screening with venous Doppler will be utilized if symptoms are present, as is also part of current routine postoperative care. Our DVT prophylaxis protocol postoperatively will be 4 weeks of aspirin 81 mg BID unless medical co-morbidities necessitate the use of other anti-coagulation. Mechanical DVT prophylaxis in the form of sequential compression devices will also be

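### The bone population is defined in two ways (sarcomas in the aims, any malignant bony tumor in the Statement of Purpose and inclusion criterion), and tumor origin does not enter the treatment comparison

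*Combined protocol and SAP*

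**What the plan says.** **Sarcoma wording.** Section I.A sets the aim in "patients undergoing radical resection of bone and soft tissue sarcomas with endoprosthetic reconstruction". The Specific Aims in II.A repeat it, comparing TXA with when it "is not used in patients undergoing radical resection of bone and soft tissue sarcomas".

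**Wider wording.** The Statement of Purpose, also in II.A, concerns "resection of malignant bony tumors with endoprosthetic reconstruction when TXA is used compared to when it is not". The inclusion criterion in II.D takes patients "undergoing wide resection of a malignant bony tumor of the lower extremity with endoprosthetic reconstruction or resection of soft tissue sarcoma measuring >5cm". The only entry in the exclusion list that turns on tumor type is "Benign tumors". Section II.B describes the bone groups without histology: "The first group (20 patients) will undergo bony tumor resection of the femur or proximal tibia and endoprosthetic reconstruction with TXA", with a matching group of 20 without TXA.

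**Use of diagnosis.** Randomization is stratified by type of resection (II.C), given as resection location in II.B. Section II.B also records pre-op diagnosis and examines its correlation with blood loss and transfusion. Section V.A adds "location of tumor, pathologic diagnosis, stage of disease" to the patient factors compared between groups. The outcome comparison itself is a Student t-test with no covariates (II.C, V.A).

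**The concern.** The inclusion sentence limits the soft tissue half to sarcoma but not the bone half. A patient with metastatic disease or myeloma in the femur, treated by wide resection and endoprosthesis, has a malignant bony tumor and no sarcoma. That patient meets II.D but lies outside the aim in I.A. The documents mention neither metastasis nor myeloma, so nothing says which statement governs.

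This matters in practice because the treating surgeon judges eligibility from chart and history (III.A, III.B) at several institutions, each with its own IRB (II.I). One site could follow the aim and another the criterion, and both could cite the protocol.

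Two things are at stake. The first is the claim: an average over an unstated mix of tumor origins is not an estimate for bone sarcoma. The second is precision: if blood loss differs by origin, an unadjusted comparison with 20 per arm carries variance that a baseline covariate could remove.

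**Working it through.** **1. The population statements side by side**

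| Place | Bone population |
|---|---|
| I.A, aim | sarcoma |
| II.A, Specific Aims | sarcoma |
| II.A, Statement of Purpose | malignant bony tumor |
| II.B, first two groups | bony tumor, no histology |
| II.D, inclusion | malignant bony tumor |
| II.D, exclusion by type | benign only |

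Two statements say sarcoma. The Statement of Purpose and the operative criterion do not, and the two readings meet inside II.A.

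**2. The plan's own figure.** II.C states power 0.9 with 20 per arm in bone. This cannot be reproduced, since alpha, sidedness, effect size and SD are not given. Back-solving with an assumed two-sided 5% test gives the standardized difference that 20 per arm would detect:
- normal approximation: d = (1.960 + 1.282) × √(2/20) = 1.025
- t-based: d = 1.052

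**3. Precision if origins are mixed (all inputs assumed).** Let m be the non-sarcoma share, s the difference in mean blood loss between origins in within-origin SDs, and let the TXA effect be the same in both. Then SD_mix = √(1 + m(1 − m)s²), and the detectable effect becomes d / SD_mix. With m = 0.30, t-based d = 1.052 and 20 per arm:

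| s | SD_mix | d / SD_mix | Power |
|---|---|---|---|
| 0 | 1.000 | 1.052 | 0.900 |
| 0.25 | √1.013 = 1.007 | 1.045 | 0.896 |
| 0.5 | √1.053 = 1.026 | 1.025 | 0.885 |
| 1 | √1.21 = 1.100 | 0.956 | 0.838 |
| 2 | √1.84 = 1.356 | 0.776 | 0.667 |

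Rounding d to 1.05 changes the last figure to 0.665. The table assumes that 0.90 was set on a sarcoma-only SD. If the planning SD came from a mixed group, the loss is already counted and power stays at 0.90.

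**4. What the average would mean.** If the TXA effect in non-sarcoma patients is a fraction r of that in sarcoma, the mixed effect is d[(1 − m) + m·r]. With r assumed to be 0.5, this is 0.875 of the sarcoma effect at m = 0.25 and 0.75 at m = 0.50. With r = 1 the two agree, but the documents give no basis for r. A sarcoma-only analysis is not a ready substitute: at d = 1.025 (normal approximation), 15 per arm gives power 0.80 and 10 per arm gives 0.63.

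**5. Chance imbalance.** For k non-sarcoma patients among 40, split 20 and 20, the hypergeometric probability that the arms differ by at least 4 such patients is 0.11 (k = 4), 0.24 (k = 8), 0.30 (k = 12), 0.33 (k = 16) and 0.34 (k = 20). This is sampling variation of the kind that the t-test's standard error already reflects. Its relevance is that a prespecified covariate would reduce it.

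**The case against.** The strongest reply is that the protocol already states a broad population. The Statement of Purpose matches II.D, the rationale speaks of musculoskeletal oncology patients generally, and randomization protects the comparison whatever the histology. On this view the sarcoma wording is loose drafting. Diagnosis is also not ignored, since II.B links it to the primary outcome and V.A checks its balance.

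Much of this stands, and it rules out several stronger readings:

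- A reader might infer that the aim is uniformly limited to sarcoma and that the result will miss the stated population. The Statement of Purpose does not support that; the population is stated inconsistently.
- A reader might infer that metastatic and myeloma cases will enter. The criterion only permits them, and requires wide resection with endoprosthesis. No case mix is given.
- A reader might call a chance imbalance in origin a bias. Under randomization it is random error.
- A reader might conclude that the bone stratum is underpowered for this reason. That needs a sizeable difference in blood loss between origins and a sarcoma-only planning SD. The documents give neither, nor any evidence that blood loss or the TXA effect depends on origin.

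What the reply leaves unanswered is that nothing says which statement governs. Correlating diagnosis with blood loss and comparing it between groups also leaves the TXA estimate itself unadjusted.

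**Conclusion.** The inconsistency is real and rests on the text alone. I.A and the Specific Aims say sarcoma; the Statement of Purpose and II.D say malignant bony tumor, with only benign tumors excluded by type. Non-sarcoma malignant bone lesions may therefore enter the 20-per-arm bone stratum. If they do, the result is valid for the patients enrolled but cannot be presented as an effect in bone sarcoma.

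The cost in power is unknown. On the assumptions in the working it runs from negligible (0.88 to 0.90 for shifts up to 0.5 SD) to material (0.84 at 1 SD, 0.66 to 0.67 at 2 SD), and it is zero if origin does not affect blood loss or the TXA effect. The case for change does not depend on these figures: it rests on the conflicting definitions and the low cost of resolving them.

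**What to change.** Make I.A, II.A and II.D name the same tumors, and state whether non-sarcoma malignant bone tumors are eligible. Keeping II.D as written:

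1. Restate the aims in I.A and II.A as malignant bone tumors, primary or metastatic, and say explicitly how myeloma is treated. The soft tissue wording can stay as sarcoma.
2. Classify tumor origin (primary or not) before randomization, from the pre-op diagnosis already collected.
3. In V.A, include origin as one prespecified covariate in the bone-stratum blood-loss comparison, and report the number of patients of each origin by arm.

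This loses no patients. It costs wording changes, one baseline field, one degree of freedom and a broader, less specific claim. The covariate helps precision if blood loss differs by origin; it does not turn the result into a sarcoma-specific estimate. If the sponsor meant sarcoma only, II.D would have to be narrowed to match the aims, with slower bone accrual as the likely price.
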